Participants were sampled at random from a population listing from AHRI/Africa Centre's surveillance. AHRI's surveillance is organized by geographically defined week blocks. Specific week blocks were chosen for this study based on the timing of AHRI's surveillance. We included respondents residing in week blocks where AHRI was scheduled to conduct its annual surveillance and HIV testing offer about 6-8 weeks after the baseline survey.

Details on the Sampling Strategy are contained in Appendix A.

We chose a target sample size of 450 individuals. The final actual sample size will be determined based on the number of successful interviews achieved within a pre-specified period, from a pre-specified roster of eligible participants. The number of eligible participants included in the study roster is based our target of 450 baseline interviews conducted. Based on prior studies of this age group at AHRI, we anticipate that we will be able to find and recruit 50- 60% of the eligible population. We anticipate that our study team is capable of conducting 60-75 interviews per week. We therefore sampled 120 individuals in each of seven week-blocks for a total of 840 individuals eligible for recruitment. The final sample size was the number of respondents successfully interviewed from the pre-specified study rosters.

With a target sample of 450 individuals, this study is powered at 80% to detect a 0.26 standard deviation difference in outcomes between the treatment and pooled control groups.

Example 1) We are powered to detect an increase in subjective (perceived) life expectancy from 50 to 54 years, assuming a standard deviation of 15 years. The baseline numbers – 50, $sd=15$ – are based on survey pre-tests conducted as part of a prior study: "Life plans of young adults in rural KZN: a qualitative study". A four-year increase would be about a quarter of the actual change in life expectancy that occurred between 2003 and 2014.

Example 2) We are powered to detect an increase in the proportion using the HIV testing voucher (or taking up the job search skills workshop) from 10% to 20%. As this is a pilot study, we are only powered to detect intervention effects if they are large.

A8. Interventions and Randomization

A8.1. Study Arms

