The study is a population-based randomized controlled trial. To reduce potential for contamination, treatment assignment will be determined at the level of the household, such that if there are multiple eligible participants per household, they will receive the same treatment. Households will be randomized to study arm *ex ante*, i.e. before going into the field. *Ex ante* randomization has two benefits. First, as a quality control, *ex ante* randomization limits the opportunity for violations of treatment assignment. Second, because the study is nested in the AHRI population surveillance, *ex ante* randomization enables us to achieve balance across study arms with respect to several baseline characteristics of interest among eligible participants. We will use a constrained randomization approach to achieve approximate balance on: sex, age, whether the person was in school, orphans status, HIV positive status, HIV negative status (unknown is the third category), and household asset quintile. These factors were selected because of their potential influence on survival expectations. (For further details on randomization procedures, please see Appendix C.)

We note that sampling and randomization will be conducted using AHRI's public use (de-identified) data. We will provide a list of public use identifiers and treatment assignments to AHRI's data management staff, and they will create an operational database to be used during data collection. Information on the characteristics above (e.g. HIV status) will never be linked with personally-identifiable information.

Participants will be randomized using a ratio of 50% active treatment, 25% attention placebo control, 25% pure control.

	Active Treatment Video	Attention Placebo Video
Arm 1, Active Treatment	X	
Arm 2, Attention Placebo Control		X
Arm 3, Pure Control		

A8.3. Blinding

Participants and interviewers

During recruitment, consent, and the first half of the baseline survey, participants and interviewers will be blinded as to the participant's treatment assignment. Randomized treatment assignment will be revealed at the moment when participants received the intervention. However, we will not indicate to the participants whether the video they see is the treatment or attention placebo video.

Researchers

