We will additionally assess balance on all primary and secondary outcomes described above that are measured at baseline.

Through linkage to the AHRI surveillance, we will additionally assess balance on: whether the person has a child; household size; distance to the nearest clinic, whether anyone in the household died from HIV in the prior 10 years; whether anyone in the household is receiving public sector ART at time of baseline.

For each baseline covariate, we will report a t-test for the null hypothesis of equal means in Arm 1 vs. Arms 2+3 (pooled).

B4. Statistical analysis of treatment effects

All statistical analyses will involve comparisons across the treatment arms described above. For each outcome, we will generate the following data:

Example Results Table (fake data)

	Sample Means				Treatment Effect Estimate (95% CI)		
	Arm 1, n=XXX	Arms 2+3, n=XXX	Arm 2, n=xxx	Arm 3, n=xxx	Crude difference	Adjusted for design variables ^a	Adjusted for design, strong predictors, and baseline imbalance ^b
Outcome 1	1.2	1.5			-0.3 (-0.5 to 0.2)	-0.3 (-0.5 to 0.2)	-0.3 (-0.5 to 0.2)
			1.7		-0.5 (-0.8 to 0.0)*	-0.5 (-0.7 to 0.0)*	-0.5 (-0.7 to 0.0)*
				1.4	-0.3 (-0.5 to 0.3)	-0.3 (-0.5 to 0.2)	-0.3 (-0.5 to 0.2)
Outcome 2							
...							
Outcome k							

^aDesign variables are those variables on which balance was explicitly assessed during randomization. ^bStrong predictors of the outcome are those factors in the baseline balance table that are adjusted differences include regression adjustment for stratifying variables, variables used in the constrained randomization, and variables that were not balanced at baseline despite randomization (p-value <0.1 in F-test).

Sample means will be reported for Arm 1, the combined control (Arms 2+3), and for Arm 2 and 3 separately. When assessing changes from baseline to follow-up, we will simply define the outcomes as within-subject “differences” to facilitate comparisons with other outcomes observed only after the intervention.

Crude comparisons of outcomes between treated and comparison arms will be assessed in linear regression models, regressing the outcome on an indicator for treatment arm and indicators for week-block, a stratification variable. We will adjust our standard errors for clustering at the household level, given that error terms without households may be correlated.

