Adjusted effect estimates. We will estimate adjusted effect estimates in multivariate linear regression models. Adjustment for covariates in an RCT has three aims[23]:

- (design variables) to obtain appropriate standard errors when conducting stratified or constrained randomization;
- (strong predictors of the outcome) to reduce residual variance in the outcome, leading to smaller standard errors and narrower confidence intervals; and
- (factors with strong baseline imbalance) to eliminate the impact of any imbalances on observed baseline factors, despite randomization

(a) In our adjusted analyses, we will include the following design variables:

- Stratification variables: week block
- Constrained randomization variables: sex, age, whether the person was in school, orphan status, HIV positive status, HIV negative status (unknown is the third category), and household asset quintile

(b) We will include the following variables believed *a priori* to be strong predictors of HIV testing and human capital investment:

- Distance to nearest clinic
- Baseline subjective life expectancy
- Baseline beliefs about lifetime HIV infection risk

(c) Finally, to eliminate imbalances on observables, we will adjust for variables with $p < 0.1$ for the t-test of differences between Arm 1 and Arm 2+3.

B5. Subgroup analyses

The informational intervention is expected to have the greatest impact for individuals with low baseline survival beliefs and for individuals with high baseline beliefs about lifetime chances of contracting HIV.

Perceived likelihood of lifetime HIV infection. The impact of the informational video is likely to vary by baseline perceived risk of lifetime HIV infection. We will assess for linear effect modification of our primary outcomes by perceived lifetime infection risk.

Baseline survival expectations. The impact of the informational video is likely to vary by baseline survival expectations, with the greatest potential shift in beliefs for individuals with previously low survival expectations. We will assess for linear effect modification of our primary outcomes by baseline subjective life expectancy.

Finally, we will assess effect modification by age (continuous, 18-25) and sex of the respondent (M/F).

B6. Robustness checks

We will subject our primary results (Arm 1 vs. Arms 2+3 for primary outcomes) to robustness checks.

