Appendix A. Sampling Strategy

Appendix B. Consent Form

Appendix C. Randomization Procedures

Appendix A. Sampling Strategy

Sampling Protocol

The sampling frame was all young adults who resided in bounded structures located in PIPSA week blocks 33-41 and were part of the AHRI PIPSA eligibility list. Young adults were defined as individuals who were 18 years or older on August 15, 2017 and were 25 years or younger on October 1, 2017. Week blocks 34-41 were selected because the AHRI surveillance was scheduled to visit these weekblocks for the annual surveillance visit and HIV testing 4 weeks after we would be there. With the AHRI surveillance 2 weeks behind schedule, we are expecting our respondents to be visited by the surveillance 4-6 weeks after the baseline survey visit. The AHRI eligibility list includes those known to reside in the surveillance and includes all those who resided in the surveillance at last visit in 2016 as well as some known to have moved in.

We randomly sampled Bounded Structures within each week block and included all individuals in each Bounded Structure. We proceeded until we had 120 individuals per Week Block, or 20 per field worker per week. We anticipate that each field worker will be able to complete 10-15 interviews per week.

The target sample size for interviews completed was 450. We assumed a 62.5% response rate, which is similar to prior studies of young adults at AHRI. Based on this response rate, we estimated that we needed to sample 720 individuals to complete 450 interviews. With a 6-field worker team and 2.5 interviews conducted per field worker per day, we project that the baseline survey will be completed in six weeks.

We sampled 8 weeks of data to ensure that if unforeseen circumstances (e.g., difficulties locating respondents, fieldworker absences, etc.) dictate lower productivity, then we will have respondents already sampled to finish fieldwork.

Our “stopping rule” for study enrollment is defined as: “Data collection will proceed for six weeks. If at the end of six weeks, we have not yet recruited 450 participants, then data collection will continue for a seventh week. If at the end of seven weeks, we have not yet recruited 450 participants, then data collection will continue for an eighth week. If after eight weeks, we still have not attained 450 participants, we will cease enrollment.”

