We have sampled 20 potential respondents per interviewer. Each interviewer is responsible for making three contacts with these respondents during the week. The total number (currently 20) of respondents allocated to each interviewer may change during the pilot stage, depending on what are acceptable workloads.

The following table describes the sampling strategy:

Week Block	Sample Size	Expected Interviews completed	Under the lower productivity scenario
34	120	75	58
35	120	75	58
36	120	75	58
37	120	75	58
38	120	75	58
39	120	75	58
40	120	0	58
41	120	0	50
TOTAL	960	450	450

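### No B4 model includes interviewer, so if interviewers differ, modest precision is lost on the outcomes they administer

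*Combined protocol and SAP*

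**What the plan says.** Section A7 gives the team's capacity: "We anticipate that our study team is capable of conducting 60-75 interviews per week". Appendix A gives its structure. There are six field workers, and the sample was drawn to match them: "We proceeded until we had 120 individuals per Week Block, or 20 per field worker per week". It adds "We have sampled 20 potential respondents per interviewer" and makes each interviewer responsible for three contact attempts with those people during the week. Allocation therefore comes before contact. Sections A8.3 and A9.2 keep interviewers blind to arm until the video is due.

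The belief and attitude items are survey questions (A9.1, A9.3, A10, B1.1). The condom and savings choices are made and recorded at the baseline visit, and the savings choice comes with a short discussion (A9.4).

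B4's crude model contains arm and week-block, with standard errors clustered by household. The adjusted models add the constrained-randomization variables, then clinic distance, baseline subjective life expectancy, baseline beliefs about lifetime HIV risk, and any variable imbalanced at p<0.1. One stated aim of adjustment is "strong predictors of the outcome) to reduce residual variance in the outcome, leading to smaller standard errors and narrower confidence intervals". Interviewer is absent from these models, from the balance list in B3 and from the robustness checks in B6.

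**The concern.** How an interviewer explains the bean task, reads the agreement items or talks about saving could move the answers of everyone that interviewer sees. If so, part of the outcome variance belongs to the interviewer, and a plan that adjusts for precision could remove it. Week-block indicators would not do this if the same six people work every block, because each interviewer then appears in all blocks. Differencing does not help the attitude index, which has no baseline, or the savings and condom choices, which are single post-video measures.

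At stake is the width of the intervals, in a trial that A7 describes as a pilot powered only for large effects. The time to settle it is before unblinding. The timeline in A12 posts the plan one day before assignments are unmasked, and a covariate chosen after that date is discretionary.

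**Working it through.** **Inputs**
- Total sample: 450 (A7, "We chose a target sample size of 450 individuals").
- Allocation: 225 active against 225 pooled control (A8.2, "Participants will be randomized using a ratio of 50% active treatment, 25% attention placebo control, 25% pure control").
- Stated power: "powered at 80% to detect a 0.26 standard deviation difference in outcomes between the treatment and pooled control groups" (A7).
- Significance level: not stated for the power calculation. Two-sided 0.05 is assumed, in line with the 95% intervals in the B4 results table.
- Interviewers: 6, hence 5 indicators (Appendix A).
- Interviewer share of outcome variance, s: not in the documents. Assumed to be 0%, 2%, 5% or 10%.

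**1. Reproduce the plan's figure.** Detectable difference = (1.960 + 0.842) × √(2/225) = 2.802 × 0.09428 = 0.264 SD, which rounds to the stated 0.26. Power at exactly 0.26 SD is 78.7%. The figure stands. It is expressed in total SD, which already contains any interviewer variance.

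**2. Remove the interviewer share.** If interviewer terms absorb a share s, the residual variance is multiplied by (1 − s) and the detectable difference by √(1 − s).

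| s | Detectable difference | Power at 0.26 SD | Equivalent N = 450/(1 − s) |
|---|---|---|---|
| 0% | 0.264 SD | 78.7% | 450 |
| 2% | 0.264 × √0.98 = 0.261 SD | 79.6% | 459 |
| 5% | 0.264 × √0.95 = 0.257 SD | 80.8% | 474 |
| 10% | 0.264 × √0.90 = 0.251 SD | 82.8% | 500 |

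**3. Count the cost of the terms.** The formula charges nothing for five extra parameters. A simulation does: 450 people, six interviewers crossed with six week-blocks, arms balanced within block, no household clustering, 2,500 replicates per value of s. The ratio of the standard error with interviewer indicators to that without is 1.006 at s = 0%, 0.997 at 2%, 0.984 at 5% and 0.962 at 10%.

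The gain is a little smaller than √(1 − s) because six interviewers show, on average, only 5/6 of the assumed variance within the sample, and the terms themselves cost about 0.6%. At 10%: √[0.90/(0.90 + 0.10 × 5/6)] × 1.006 = 0.957 × 1.006 = 0.962. Step 2 is therefore slightly optimistic. Below about 2% there is almost nothing to gain.

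**4. Sort the outcomes.**
- Administered and recorded at the interview: savings allocated, condoms purchased, immediate post-video beliefs and attitudes, and the 2-month beliefs and attitudes.
- Recorded elsewhere: voucher use (pharmacies), home testing (surveillance linkage) and workshop attendance (workshop roster). The baseline visit makes the voucher and workshop offers but does not measure uptake.
- Mixed: the composite, where savings is one item of three. As an illustration, if the items had equal variance and were uncorrelated, a 10% share in savings alone would be 10%/3 = 3.3% of the composite.

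**The case against.** The strongest reply is that no between-interviewer variation is reported, so the loss rests on a quantity nobody has observed, and a short covariate list chosen in advance is legitimate. That stands. The point is conditional, and aiming to reduce variance does not oblige a plan to use every candidate covariate.

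Two further objections also stand. First, the primary belief and attitude outcomes are taken at 2 months, and the documents do not say who conducts that survey. If the same interviewer returns, a stable effect cancels in the life-expectancy change. If someone else does, baseline indicators cannot absorb the follow-up effect. Second, baseline subjective life expectancy and HIV risk beliefs are already B4(b) covariates and would carry some of any baseline interviewer effect, so the gain for belief outcomes may be below the table.

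Storage of the allocation as data is inferred from the roster system, not stated. Appendix A says workloads may change in the pilot stage and allows for absences.

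A reader might infer that chance imbalance of interviewers between arms biases the estimates. The documents do not support that. Arms were fixed before fieldwork, interviewers are blind until the video, and chance imbalance is part of what the confidence interval describes.

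**Conclusion.** The omission is real, and its likely effect is modest. No specified model, balance list or robustness check includes interviewer, and for interviewer-administered outcomes a covariate fixed before treatment could recover some precision. At an assumed 2% to 10% of variance, the detectable difference moves from 0.264 SD to between 0.261 and 0.251 SD. At 0% the terms cost about 0.6% in standard error. On A7's SD of 15 years for subjective life expectancy, the largest of these changes is 0.013 × 15, or about 0.2 years. The sizes assume that the terms absorb the whole share and that a stable team of six works across week-blocks.

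Three stronger readings are tempting and do not hold:
- That interviewer variation is known. Nothing in the documents measures it.
- That the 0.26 SD power figure is wrong. It is reproduced and is stated in total SD.
- That every primary outcome is affected. HIV testing is not measured by the interviewers, and the composite is affected mainly through its savings item.

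This is an inexpensive improvement and does not correct an error.

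**What to change.** Add one sentence to the B4(b) precision covariates: for interviewer-administered outcomes, include indicators for the interviewer allocated on the field roster. B4(a) is the wrong place, because it is reserved for variables used in the randomization.

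- **Outcomes covered:** savings allocated, condoms purchased, immediate post-video beliefs and attitudes, and the composite through its savings item.
- **2-month belief and attitude outcomes:** use the interviewer allocated for the follow-up visit if that differs from the baseline one, provided the follow-up allocation was made without regard to arm.
- **Which interviewer:** the allocated one, not the one who completed the interview, so that the covariate cannot depend on arm.
- **Not required:** voucher use, home testing and workshop attendance.
- **Unchanged:** clustering of standard errors.

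Placed in B4(b), the terms affect only the fully adjusted estimate. If assignments have already been unmasked, report the analysis as a labelled sensitivity analysis instead.

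The cost is the wording, about five degrees of freedom out of about 450 (more if the team changed), and a standard error about 0.6% larger if interviewers turn out not to differ. No new data collection is needed if the allocation can be retrieved from the field rosters, which should be confirmed first.

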The researchers will be blinded to the randomization status of participants throughout the data collection, extraction, and cleaning/quality control process, up until the date when randomized assignments are unmasked. To maintain blinding of treatment assignments vis-à-vis the research team during the study, we will use the following procedures:

- Treatment assignment will be stored as a hidden field in the REDCap database. I.e. during the baseline survey it will generate a pop-up message telling the interviewer to show the participant the active treatment video, active control video, or no video, however this field will not be visible to anyone on the research team.
- The treatment assignment field will not be exported during routine quality control procedures.
- Treatment assignment will be extracted along with study ID into its own table and will not be merged with any of the other data until randomization is unblinded.
- Randomization will be unblinded only after the final Pre-Analysis Plan is posted to www.clinicaltrials.gov. In developing our pre-analysis plan, we conducted some descriptive analysis of the blinded baseline pre-intervention survey data. Additionally, we monitored overall levels of uptake of the HIV testing voucher and job search training workshop in order to determine potential statistical power with these outcomes. For guidance on using baseline data to inform Pre-Analysis Plans, see Olken (2015).
- We will submit an update to our clinicaltrials.gov study profile after treatment assignment is unblinded, noting the date when we have done so.

As this is a short (4-month) pilot study and the intervention is minimal risk, we do not have a DSMB and do not have stopping rules for the trial based on preliminary analysis of efficacy.

A9. Baseline interview and intervention

The baseline survey visit is designed to take about 1.5 hours, and consists of the following sub-components:

A9.0. Recruitment and Informed Consent

Potential respondents will be recruited via visits to their homesteads. Permission will be obtained from the head of household to enter and to speak to the sampled participant. The study will be described and participants will provide written informed consent to participate in the study, including the baseline visit, a follow-up visit, and permission to link with demographic surveillance data. See Appendix B for the approved consent form.

A9.1. Survey module

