Appendix C. Randomization Procedures

Variables Randomized. Study participants are randomized with respect to:

- 1) Intervention video vs. no intervention video
- 2) Pure control vs. attention placebo control (among those randomized to no intervention video)
- 3) 20 Rand vs. 5 Rand cost to reserve spot at job search skills workshop
- 4) Male-vs.-female-oriented HIV transmission questions

1. Intervention video vs. no intervention video

Level of randomization. Individuals are randomized to video intervention vs. control. Randomization is at the bounded structure level, so that all respondents within a bounded structure get the same treatment.

Stratification. Randomization is stratified by weekblock to ensure approximately equal numbers of treated and controls within weekblocks.

Constrained (restricted) randomization. The AHRI data contain robust information on baseline covariates. However, because randomization is at the level of the bounded structure, it was not possible to stratify by individual characteristics. Instead, we use a constrained (aka restricted[25]) randomization approach. For the primary analysis – comparison of intervention video vs. no intervention video, we constrained randomization to force balance on the following characteristics: sex, age, whether the person was in school, orphan status, HIV positive status, HIV negative status (unknown is the third category), and household asset quintile. We randomized the intervention treatment assignment (intervention video vs. no intervention video) 3078 times using different randomization seeds. Each time, we assessed balance on key characteristics through a t-test (i.e regression of treatment assignment on the covariate). All randomization seeds that lead to a maximum t-test value greater than 1.68 ($p<0.1$) were excluded. This excluded 62% and retained 38% of the seeds (1060 seeds). We then randomly selected two seeds from these 1060 acceptable seeds. One was used to randomize the video, the other was used to randomized the incentive for the job search skills workshop. We assessed correlation of these two interventions and re-randomized if the Chi2 p-value for the cross-tab was less than 0.5 (see tables below).

2. Pure control vs. attention placebo control (among those randomized to no intervention video)

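### A7's 80% power for 0.26 SD matches 450 independent, fully observed people, but assignment is by household or structure and primary outcomes 3 and 4 come from the 2-month survey

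*Combined protocol and SAP*

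**What the plan says.** **Power.** A7 states that with 450 individuals "this study is powered at 80% to detect a 0.26 standard deviation difference in outcomes between the treatment and pooled control groups". The size of the study roster "is based our target of 450 baseline interviews conducted". Two examples follow: a rise in subjective life expectancy from 50 to 54 years with SD 15, and a rise from 10% to 20% in voucher use or workshop attendance. A7 then adds: "As this is a pilot study, we are only powered to detect intervention effects if they are large". It names no alpha, ICC or design effect, retention rate or model.

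**Unit of assignment.** A8.2 says that "treatment assignment will be determined at the level of the household". Appendix C says: "Randomization is at the bounded structure level, so that all respondents within a bounded structure get the same treatment". Appendix A says: "We randomly sampled Bounded Structures within each week block and included all individuals in each Bounded Structure". B4 plans standard errors clustered by household.

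**Primary outcomes (B1.1).**
- Outcomes 1 (HIV testing by voucher or at home) and 2 (the behaviour count) use voucher returns, surveillance testing, workshop attendance and the baseline savings choice. B1.2 scores people who were not at home for surveillance testing as 0.
- Outcome 3 (change in subjective life expectancy) and outcome 4 (attitudes index) are measured at the 2-month survey. B1.1 says that outcome 4 has no baseline measurement.

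**Attrition.** The attrition section plans inverse probability weighting if more than 20% are lost. No expected loss is given.

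**The concern.** A7 is the passage a reader will use to judge which effects this trial could detect, and 0.26 SD is given there as one figure for all outcomes. Two features of the plan's own design appear to be left out of it. Participants in the same household or structure are not independent replicates of the assignment, and B4 recognises this in its standard errors. In addition, two of the four primary outcomes are observed only in people who complete a second interview, while A7 counts first interviews.

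What is at stake is how a null result is read. There is no multiplicity adjustment across the primary outcomes, so each stands alone and a null on any of them will be set against A7. If the true detectable difference is larger than 0.26 SD, a reader would take a null as stronger evidence of no effect than it is.

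**Working it through.** **Inputs from the documents.** 450 people (A7). Half are assigned to the intervention video and half to the two control arms pooled (A5, A8.2), so 225 versus 225. Two-sided 5% is inferred from the 95% intervals in B4's example table, since A7 does not state it.

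**Inputs assumed here.** The documents give no ICC, number interviewed per unit or retention. Design effect DE = 1 + (m − 1) × ICC. With m = 1.25 and ICC 0.05 to 0.4, DE is 1.01 to 1.10; with m = 1.5 it is 1.03 to 1.20. The range used is 1.01 to 1.2. Retention f is set at 100%, 90% and 80% as examples; none of these is a bound.

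**Formulas (normal approximation).**
- Effective number: N_eff = 450 × f / DE.
- Minimum detectable difference (MDE) at 80% power: (1.960 + 0.842) × √(4 / N_eff) SD.
- Power at 0.26 SD: Φ(0.26 / √(4 / N_eff) − 1.960).

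**Step 1: reproduce A7.** With f = 1 and DE = 1, √(4/450) = 0.0943. MDE = 2.802 × 0.0943 = 0.264 SD. Power at 0.26 SD = Φ(2.758 − 1.960) = 78.7%. Allowing for rounding of the effect size, this is A7's figure. There is little slack: power at 0.26 SD falls below 78% once N_eff drops below about 442.

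**Step 2: add clustering and retention, no covariates.**

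| Retention | DE | N_eff | MDE (SD) | Power at 0.26 SD |
|---|---|---|---|---|
| 100% | 1.00 | 450 | 0.264 | 78.7% |
| 100% | 1.01 | 446 | 0.265 | 78.3% |
| 100% | 1.10 | 409 | 0.277 | 74.8% |
| 100% | 1.20 | 375 | 0.289 | 71.1% |
| 90% | 1.00 | 405 | 0.278 | 74.4% |
| 90% | 1.10 | 368 | 0.292 | 70.3% |
| 80% | 1.00 | 360 | 0.295 | 69.4% |
| 80% | 1.10 | 327 | 0.310 | 65.2% |

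The 100% rows apply to all four primary outcomes. The 90% and 80% rows apply to outcomes 3 and 4 only.

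**Step 3: what covariates would have to recover.** If covariates explain a share R² of the outcome variance, N_eff is divided by 1 − R². Returning to 0.264 SD needs R² = 1 − f/DE. For DE 1.01 to 1.2 that is 1% to 17% at full follow-up, 11% to 25% at 90% retention and 21% to 33% at 80%.

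**Step 4: A7's examples.**
- Example 1 as stated: 4/15 = 0.267 SD, power 80.7%. B4's fullest model includes baseline subjective life expectancy, so the residual SD is 15 × √(1 − r²), where r is the assumed correlation between baseline and 2 months. For r = 0.3 to 0.5 and DE = 1, power is 84% to 90% at full follow-up and 76% to 83% at 80% retention. At DE 1.2 these become 77% to 85% and 68% to 76%. B4's crude model on the change score has SD 15 × √(2(1 − r)). At the same correlations, full follow-up and DE = 1, it gives 67% to 81%.
- Example 2 (10% versus 20%, pooled-variance formula, 225 per group): 84.6%. It stays at or above 80% up to a design effect of about 1.13.

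**The case against.** Several points on the other side are fair.

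- **Alpha.** A7 does not say two-sided. At one-sided 5%, 360 people already give an MDE of 0.262 SD, so the match to 450 fully observed people depends on the two-sided reading. That stands as a condition. B4's 95% intervals and the no-effect null hypotheses make two-sided the natural reading.
- **Covariates.** B4 adjusts for the design variables, clinic distance, baseline life expectancy and baseline HIV-risk beliefs, and this could recover some or all of the loss. That stands too, and plausibly for outcome 3. But A7 claims no such credit and does not say which B4 model it assumes. Outcome 4 has no baseline value of its own, so recovery there is least assured.
- **Small clusters.** Only interviewed people aged 18 to 25 count, so the design effect may be close to 1. At 1.01 the cost is 0.4 points of power. The retention point for outcomes 3 and 4 does not depend on clustering.
- **Sample size not fixed.** A7 expects to recruit 50% to 60% of 840, which is 420 to 504 people, or 76% to 83% power at 0.26 SD under its implied assumptions. This moves the figure both ways and does not supply the missing allowances.
- **Pilot status and timing.** A7 warns that only large effects are detectable, and by the document's date both surveys were finished. Enrolment cannot change, and B4's confidence intervals remain the main protection against over-reading a null. This limits the consequence, but the warning does not correct the 0.26 SD.

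A reader might infer that A7 contains a calculation error. It does not: the figure reproduces under the assumptions above.

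**Conclusion.** The point holds as one about a stated figure that leaves out two features of the plan's own design. At two-sided 5% and before any covariate gain, 0.26 SD at 80% power is too favourable: slightly to moderately for all four primary outcomes through clustering, and more for outcomes 3 and 4 through loss before the 2-month survey.

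On the assumed ranges, power at 0.26 SD is 78% to 71% from clustering alone, 74% or 69% from 90% or 80% retention alone, and 65% with 80% retention and a design effect of 1.10. The direction follows from the documents, given positive within-unit correlation and some loss to follow-up. The size does not, because ICC, cluster size and retention are all assumed.

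The tempting stronger reading is that the trial is underpowered. The documents do not support that for every planned analysis. Example 2 tolerates a design effect of about 1.13, Example 1 keeps 80% in many of the covariate-adjusted cases, and the attrition problem does not reach outcomes 1 and 2.

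**What to change.** Restate the detectable difference in A7, or in a short note in Part B, separately for each primary outcome at two-sided 5%. Give:

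- the randomisation unit (household or bounded structure, so that A8.2, Appendix C and the B4 clustering level agree), the mean number interviewed per unit, an assumed ICC and the resulting design effect;
- for outcomes 3 and 4, the expected or pooled blinded 2-month retention;
- the B4 model assumed and the variance its covariates are expected to explain, noting that outcome 4 has no baseline value.

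At minimum, add one sentence: the 0.26 SD assumes two-sided 5%, independent participants, full follow-up and no covariate adjustment, and the detectable difference for outcomes 3 and 4 is larger if independence or full follow-up fails and covariates do not make up the loss.

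The cost is one sentence or one paragraph, plus pooled counts that do not require unblinding. Sample size, tests and estimates stay as they are. The only downside is a slightly less favourable stated figure. A worked example for combined HIV testing, or a report of the uptake monitoring mentioned in A8.3, would be useful but is not required.
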